### **3.7. Other/Persistence with treatment endpoints**

- Performance status  
We will use the two-sample Wilcoxon test to evaluate between-group differences in ECOG PS.
- Cumulative rates of remaining on any anti-coagulation therapy at 3 and 6 months
- Cumulative rates of remaining on the assigned (and/or selected in the case of the preference cohort) anti-coagulation therapy at 3 and 6 months.
- 

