## 8.4 Baseline Study Questionnaire

The **Baseline Study Questionnaire** will collect: patient-reported ECOG performance status, SF-12 HR-QOL (the Optum SF-12 Health Survey uses 12 questions to measure functional health and well-being from the patient's point of view), information about the index VTE, cancer type/status, co-morbidities, influence of insurance coverage on decision to be participate, and demographics.

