## 8.6 Follow-up Study Questionnaires

The **Follow-up Study Questionnaire** (administered at 3-months post-enrollment and again at 6-months post enrollment) will collect: patient-reported ECOG performance status, SF-12 HR-QOL, anticoagulation therapy information including dose and adherence, ACTS anticoagulation

therapy burden (the Anti-Clot Treatment Scale (ACTS) is a 15-item patient-reported instrument of satisfaction with anticoagulant treatment), VTE recurrence, and bleeding.

It is the **Central Study Coordinator's responsibility** to administer the Follow-up Study Questionnaires to the participant.

**Timing:** The Follow-up Study Questionnaire will be administered once at 3-months (+/- 1 month) after enrollment and once at 6-months (+/- 1 month) after enrollment.

- If a participant has withdrawn consent to participate in the patient questionnaire component of this study, then do not administer any additional Follow-up Study Questionnaires.

The **Central Study Coordinator** will contact the participant via phone, internet, and/or postal mail depending on participant preferences.

- To administer the questionnaire via SECURE WEBLINK: The Central Study Coordinator will email the secure, individualized questionnaire link to the participant. The participant will enter his/her responses directly into REDCap using the link provided.
- To administer the questionnaire via PHONE: The Central Study Coordinator will follow the phone script found in Appendix: Follow-up Study Questionnaire – for administration via phone". The Central Study Coordinator will enter the participant's responses into REDCap.
- To administer the questionnaire via POSTAL MAIL: The Central Study Coordinator will print and mail the paper version of the Follow-up Study Questionnaire along with a prepaid return envelope to the participant's mailing address. The Central Study Coordinator will enter the participant's responses into REDCap, and keep the original paper copy in the participant's central study file.

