## 8.7 Medical Record Abstraction

At six months after enrollment (or at the time of the participant's death, whichever occurs first), the site will conduct and submit the Medical Record Abstraction Form via REDCap. The information needed to fill out the Medical Record Abstraction Form can be found in the participant's medical record.

The Medical Record Abstraction Form will collect the following types of information:

- Demographics (age at diagnosis, current age, gender, race, ethnicity, marital status)
- Clinician-reported ECOG performance status
- Height, weight, BMI (body mass index)
- Tobacco history (current use/former use/never use and pack year history)
- Comorbidities using the Katz scale
- VTE type, location, presentation, history
- Tumor site, histology, and metastatic sites of disease
- Presence of brain metastases
- Lab Values (hepatic, renal, platelet counts, CBC [complete blood count], red cell count)
- Other treatment types (hormone, chemo, surgery, radiation)
- Bleeding, recurrent VTE, survival
- Anticoagulation therapy selection, doses, modifications
- Medication history during time on study.

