## 3. Analysis methods and presentation

### 3.1. General principles

Analysis will be performed on the preference cohort and the randomized cohort separately. Where appropriate, variables will be summarized descriptively (frequency counts and percents for categorical variables, and counts, means, standard deviations (SD), medians, minimums, maximums, etc., for continuous variables) for two treatment groups – DOACs and Control. The primary analysis cohort is the randomized cohort. The secondary analysis cohort is the preference cohort. Using meta-analysis technique, the results from two cohorts will be combined.

We will construct 90% two-sided confidence intervals (CI) for the between-group comparisons for the analyses of VTE, bleeding, and mortality. A 90% two-sided CI corresponds to conducting a statistical test at a one-sided 5% significance level. For the other analyses, all confidence intervals, statistical tests, and resulting p-values will be reported as two-sided and assessed at the 5% significance level. If the computed lower confidence bound for proportion variables is less than -1, then the lower bound is defined as -1. If the computed upper confidence bound for proportion variables is greater than 1, then the upper bound is defined as 1.

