### 3.4. Baseline demographic and disease characteristics

Baseline patient characteristics and disease characteristics listed below will be summarized using descriptive statistics by group. The two-sample Wilcoxon test will be used for between-group comparisons of continuous variables and ordered categorical variables, and Fisher's exact test will be used for nominal categorical variables.

List of the variables:

- Age at enrollment [year]
- Age category (<65, >=65 year old)
- Sex (Male/Female)
- Race (Native American or Alaska Native/Asian/Black or African American/Native Hawaiian or other Pacific Islander/White/Unknown)
- Ethnicity (Hispanic or Latino/Not Hispanic/Unknown)
- Height [cm]
- Weight [kg]
- BMI
- Education level (Grade school or less/high school or GED/Some vocational, business or trade school/some college/college/some graduate school/graduate or professional degree)
- Whether out-of-pocket costs of anti-clotting drugs affect decision to participate in the study (not at all/a little/moderate/quite a bit/extremely)
- Payment (Private insurance/Medicare/Medicaid/Military or Veterans Sponsored/Self Pay/Other/Unknown)
- ECOG performance status (0/1/2/3/4)
- Smoking status (current/former/never)
- Cancer ever metastasized (Yes/No)
- HighlyThrombogenetic Tumors (Yes/No)
- Indwelling Central Venous Catheters (Yes/No)
- Thrombocytopenia (Yes/No) (<150,000/mm^3)
- Creatinine Clearance [ml/min] (Gender-specific Normal/abnormal)
- Albumin [g/dL] (<3.5mg/dL vs. >=3.5mg/dL)
- Self described global health status at baseline (excellent/very good/good/fair/poor)
- Current cancer Type (solid cancer vs hematologic cancer)
- Current cancer Subtype (Leukemia/Lymphomas/Blood Disorders, Breast, Gastrointestinal and Digestive, Gynecologic, Head and Neck, Neurological (Brain), Sarcoma, Skin/Melanoma, Thoracic (Chest/Lung), Genitourinary, Other)
- AJCC cancer stage at diagnosis (0, I, II, III, IV, Not applicable)
- Blood clot type (PE, DVT, Both, Unknown)
- The part(s) of the body where the blood clot found
  - Lung (Yes/No)
  - Leg (Yes/No)
  - Arm (Yes/No)

- Other (Yes/No)
- Site of index VTE diagnosis (inpatient hospital stay/outpatient appointment/emergency department/home/other)
- Site of index VTE first treatment (inpatient hospital stay/outpatient appointment/emergency department/home/other)
- First index VTE treatment prescribed (Warfarin/Dalteparin/Enoxaparin/Fondaparinux/Heparin/Other oral medication/Other injectable medication/Unknown)

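### ECOG performance status is compared between arms without using the baseline ECOG already collected, which gives up precision on a low-stakes endpoint

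*Combined protocol and SAP*

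**What the plan says.** The method for performance status is a single sentence, the same in SAP 3.7 and protocol 13.3.6: "We will use the two-sample Wilcoxon test to evaluate between-group differences in ECOG PS". It names no covariate, visit, source of the ECOG score or effect measure, and does not say whether the level or the change is tested.

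ECOG is measured more than once:

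- Protocol 8.4: the baseline questionnaire "will collect: patient-reported ECOG performance status, SF-12 HR-QOL". It is completed before protocol treatment starts.
- Protocol 8.6: the questionnaire at 3 and at 6 months collects "patient-reported ECOG performance status, SF-12 HR-QOL, anticoagulation therapy information including dose and adherence".
- Protocol 8.7: the record abstraction adds "Clinician-reported ECOG performance status".
- SAP 3.4 lists ECOG, coded 0 to 4, among the baseline variables summarized and tested between groups, without saying who reports it.

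The error rate comes from SAP 3.1. Outside VTE, bleeding and mortality, the rule is "For the other analyses, all confidence intervals, statistical tests, and resulting p-values will be reported as two-sided and assessed at the 5% significance level".

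The covariate-adjusted model (SAP 3.5.2.3, item 5) is listed under the primary endpoint. SAP 3.6.2 extends it to bleeding, but no sentence extends it to ECOG. The propensity-score step (SAP 3.5.2.3, item 3) concerns the VTE rate. By contrast, the SF-12, taken from the same questionnaires, is analysed as change from baseline (SAP 3.6.2).

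**The concern.** Baseline performance status is likely to predict later performance status well. A comparison of follow-up scores that ignores it treats predictable between-patient variation as noise, so the interval is wider and the power lower than the data already collected would allow.

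A second, conditional cost concerns comparability. The SAP makes the modified ITT set primary because a number of patients did not receive the treatment they were assigned (SAP 3.2), and it also analyses the non-randomized preference cohort (SAP 3.1). In those sets the arms need not be comparable at baseline. An unadjusted test then passes any baseline ECOG difference into the follow-up comparison.

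**Working it through.** **Plan's own figure.** There is none to reproduce. The documents give no sample size, power, effect size or baseline to follow-up correlation for ECOG. The powers of 0.900 and 0.756 in SAP 2.5 concern VTE recurrence.

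**Inputs from the documents.** 671 randomized 1:1 (SAP 2.5 and 2.2), so about 336 per arm. This is an upper limit, because protocol 7.0 tolerates missing questionnaires. Two-sided alpha is 0.05 (SAP 3.1).

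**Assumed inputs.** Correlation rho of 0.3 to 0.7 between baseline and follow-up ECOG, and the reading that the test is on the follow-up level of patient-reported ECOG.

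**Step 1: precision.** Adjusting for baseline multiplies the variance of the arm difference by 1 − rho². For an effect with 80% unadjusted power, the standardized effect is 1.96 + 0.8416 = 2.8016, so

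adjusted power = Φ(2.8016 / √(1 − rho²) − 1.96).

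The equivalent unadjusted sample size is 672 / (1 − rho²).

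| rho | variance ratio | adjusted power | equivalent unadjusted N |
|---|---|---|---|
| 0.3 | 0.91 | Φ(0.977) = 84% | 738 |
| 0.5 | 0.75 | Φ(1.275) = 90% | 896 |
| 0.7 | 0.51 | Φ(1.963) = 98% | 1318 |

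**Step 2: does this carry over to a coarse ordinal score?** The formula is for a linear model, so it was checked by simulating a five-level score.

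- Rank ANCOVA, 336 per arm, 3,000 runs per setting, assumed ECOG distribution 30/42/20/7/1%, latent shift 0.225 SD. The Wilcoxon test had 76 to 77% power. Rank ANCOVA with baseline ECOG had 82%, 88% and 95% at observed Spearman correlations of 0.34, 0.52 and 0.65.
- Proportional-odds model with baseline category, 220 per arm, 600 runs per setting, assumed distribution 25/45/20/8/2%. Power was 79% (Wilcoxon) against 82% (adjusted) at rho 0.3, 81% against 87% at 0.5, and 82% against 95% at 0.7. The Monte Carlo standard error is about √(0.8 × 0.2 / 600) = 1.6 points per estimate, so the 3-point gain at rho 0.3 is not sharply estimated.

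With no effect and no baseline shift, all methods rejected about 5% of the time.

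**Step 3: would a change score do instead?** In the first simulation, a Wilcoxon test on change had 67%, 81% and 93% power. At the lowest correlation that is worse than no adjustment at all. The baseline value should enter as a covariate.

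**Step 4: sets where randomization no longer protects comparability.** Suppose there is no treatment effect, 300 patients per arm and a baseline shift of 0.15 SD. That shift is assumed; no document gives one. The unadjusted Wilcoxon test rejected about 11%, 17% and 24% of the time at latent rho 0.4, 0.6 and 0.75 (2,000 runs each). Rank ANCOVA rejected between 5.3% and 6.5%. By construction, all of the imbalance here ran through baseline ECOG. In practice adjustment removes only the part that baseline ECOG captures.

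**The case against.** The strongest reply is that the Wilcoxon test is valid and the stakes are small. Most of that stands. Randomization is unstratified (protocol 6.1.1), but 1:1 allocation balances baseline ECOG in expectation, and the test's 5% error rate already allows for chance imbalance in the full randomized set. SAP 3.4 also tabulates and tests baseline ECOG, so an imbalance would be seen. ECOG is not among the primary or secondary endpoints, appears in no objective, and has no power target. What remains is an efficiency gain from data already in hand.

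It can also be said that SAP 3.7 never states that follow-up patient-reported ECOG is what is tested. That is correct. It is the natural reading, since the patient questionnaires are the only source described at both 3 and 6 months, but it is still a reading. Likewise, protocol 8.4 and 8.6 give no scale; the 0 to 4 coding appears only in SAP 3.4.

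A reader might go further and infer two things that the documents do not support.

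- *That the comparison is biased.* In the full randomized set it is not. In the modified ITT and preference sets bias is possible, but no baseline ECOG difference is reported and SAP 3.7 names no population.
- *That patients who die are dropped, so the arm with more deaths could look better.* The plan does not say they are dropped. Protocol 13.7 promises complete-case and multiple-imputation analyses for missing values in general, and the abstraction form, which includes clinician-reported ECOG, is completed at death if that comes first (protocol 8.7). The handling of deaths for ECOG is unspecified, and any demonstration of a reversed direction needs mortality figures that the documents do not contain.

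**Conclusion.** The point holds as a matter of precision. On the natural reading, an ECOG effect with 80% power under the planned test would have about 84%, 90% or 98% power with baseline adjustment at rho 0.3, 0.5 or 0.7. The gain is modest at the low end and substantial from about 0.5 upward. It rests on an assumed correlation, and the simulations rest also on assumed score distributions and numbers of scored patients.

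In the full randomized set the cost is precision only. In the modified ITT and preference cohorts, adjustment would also remove whatever selection imbalance baseline ECOG captures, of unknown size. Severity is low: no primary or secondary endpoint conclusion is affected.

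**What to change.** In SAP 3.7 and protocol 13.3.6:

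- State that the analysis variable is patient-reported ECOG at 3 months and at 6 months.
- Analyse each visit with a proportional-odds model with arm and baseline patient-reported ECOG as covariates, and report the common odds ratio with its 95% CI. Rank ANCOVA with the same baseline covariate is an acceptable alternative.
- Keep the unadjusted Wilcoxon test as a sensitivity analysis.

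The cost is a few sentences and one standard model, with no new data. The small downside is the proportional-odds assumption, against which the retained Wilcoxon test is a check. Patients without a baseline questionnaire need a stated rule; the multiple imputation in protocol 13.7 can serve.

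Ranking death as the worst category should not be part of the main change. It turns a functional-status endpoint into a composite of death and function, and so changes the estimand. At most it belongs in an optional sensitivity analysis, since mortality already has its own analysis in SAP 3.6.2.

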## **3.8. Safety endpoint evaluation**

### **3.8.1. Safety endpoints**

- Major bleeding (primary protocol safety endpoint)
- Clinically significant non-major bleeding
- Any bleeding (major bleeding and clinically significant non-major bleeding and nuisance bleeding)
- Other Serious Adverse Events

For this trial, “Expedited Serious Adverse Event” reporting is required using the SAE Report Form in REDCap. Adverse event reporting begins at enrollment and should continue until 30 days after the last administration of on-study protocol treatment. SAEs for other endpoints are reported via the following guidelines:

- Grade 1 or 2 adverse events that resulted in hospitalization for 24 or more hours,  
or
- Grade 3, 4, or 5 adverse events regardless of hospitalization

### **3.8.2. Analyses for safety endpoints**

The analysis plan for major bleeding and any bleeding are outlined in section 3.6.2. Incidence of all other SAEs will be summarized by cohort, arm, grade, and type of SAE. Fisher's exact test will be performed to compare the event rates.

### 3.9. Subgroup Analyses

We will perform subgroup analyses to investigate the potential heterogeneity of treatment effects. For each subgroup, we will perform the same analyses described in the previous sections. The treatment effect by subgroup will be summarized by point estimates and corresponding 90% confidence intervals. We will create forest plots to display those results. This analysis will be performed with an exploratory purpose; we will not adjust for multiple comparisons.

First, we will focus on the 3 key subgroups described below because these groups are common, and decision making in these contexts is challenging for oncologists and patients. These 3 subgroups represent populations of particular interest for clinical decision makers.

#### 3.9.1. Pre-specified subgroup 1: Patients with Highly Thrombogenic Tumors

We anticipate that at least 300 patients with lung (NSCLC and small cell), pancreas, esophagogastric and ovarian cancers are represented in the study sample. These patients have an even higher risk of VTE than cancer patients in general. Based on anticipated higher adherence rates to DOAC therapy and the likelihood of warfarin failures in the LMWH/warfarin arm, we anticipate a slight advantage for DOACs over the standard care arm. As planned for the full cohort analysis, we will only test for superiority in the subgroup if noninferiority is met.

#### 3.9.2. Pre-specified subgroup 2: Indwelling Central Venous Catheters

We anticipate that a subgroup of approximately 500 study participants will have an indwelling central venous catheter in place at the time of enrollment. This recruitment should not be challenging given how commonplace use of these catheters has become in routine oncology practice. The rate of VTEs is expected to be slightly higher for patients with a central venous catheter due to the excess risk of upper extremity clots.

#### 3.9.3. Pre-specified subgroup 3: Thrombocytopenia

We will consider the subgroup of participants with baseline platelet counts less than 150,000/microliter. Thrombocytopenic cancer patients face high risk of VTE but also face higher risks of bleeding. In this setting, the choice of anticoagulation strategy is challenging.

#### 3.9.4. Other preplanned subgroups

We will perform the same analysis for the following subgroups with an exploratory purpose.

- Sex (Male, Female)
- Age (below 65, equal or greater than 65)
- Participants with central nervous system (CNS) tumor involvement
- Participants with liver metastases
- Participants with albumin <3.5mg/dL
- Participants treated with bevacizumab
- Participants incidentally detected VTE on routine imaging studies (versus symptomatically detected VTE)
- Participants with metastatic disease (versus completely resected disease or no radiographic evidence of tumor)
- Participants with >80% days of persistence with anticoagulant therapy (vs. >50-80% vs. <=50%) by participant estimate

- Participants with >80% days of persistence with anticoagulant therapy (vs. >50-80% vs. <=50%) by medical record abstraction/dose refills
- Solid tumors versus hematologic malignancies

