## 12.6 New or Recurrent VTEs on Study

If a patient experiences a new or recurrent VTE while on study, sites should follow these steps:

- First and foremost, please make anticoagulation treatment decisions that are in the best interest of the patient. Sites are NOT required to stick with the anticoagulant to which the patient was assigned per protocol. Sites can switch anti-clot drugs (to an anti-clot drug from Arm 1, Arm 2, or neither arm), dose modify drugs, or discontinue drugs. **Select the strategy** that is best for the patient in view of the totality of their care.
  - **For patients on treatment with a DOAC:** From a standard of care approach, if your patient was assigned to treatment with a DOAC and they develop a new VTE while taking the DOAC without interruption, it is recommended that they switch to a parenteral agent/standard of care.
  - **For patients taking warfarin:** If the patient is on warfarin, we suggest that they switch to a parenteral agent. If the patient develops a new VTE while taking full dose parenteral agent without interruption then we suggest escalating the dose to 125% as is convention based on small study results
- If the participant is taken off protocol treatment, please:
  - have a member of your study staff (CRA) log into REDCap and fill out a **"Change in Enrollment Status/Off-Study Form."**
    - On the form, please select the 3rd response option which says:

“CLINICIAN WITHDRAWAL: Clinician took participant off protocol treatment. Please note that after taking a subject off protocol treatment, study questionnaires and patient-reported drug diaries continue through the 6th month. Site study staff should complete the Medical Record Abstraction Form at the end of the 6th month no matter how long the subject actually received protocol-directed anticoagulation.”

- There are no study questionnaires or medical record tracking that extend beyond 6 months.

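### Treatment effects estimated within strata of 6-month persistence are partly sorted by outcome, and the SAP leaves open the definition that sets the size of the bias

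*Combined protocol and SAP*

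**What the plan says.** SAP 3.9.4 opens its list with "We will perform the same analysis for the following subgroups with an exploratory purpose". The list starts with sex and age and includes two persistence variables. One is "Participants with >80% days of persistence with anticoagulant therapy", set against >50-80% and at most 50%, as estimated by the participant; the other uses the same cut-offs "by medical record abstraction/dose refills". Protocol 13.5.1.4 carries the same list. Under SAP 3.9, each subgroup gets the analyses of the preceding sections, point estimates with 90% intervals, and a place in the forest plots. SAP 3.9 adds: "This analysis will be performed with an exploratory purpose; we will not adjust for multiple comparisons".

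Two of the key subgroups are fixed in time: catheters at enrollment (SAP 3.9.2) and baseline platelets (SAP 3.9.3). The persistence rows have no landmark, no cut-off at the first event and no rule for deaths in the day count.

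Protocol 11.5 has patients report, at 3 and 6 months, the days off all anticoagulants and the days on each type. Records are abstracted at 6 months. SAP 3.7 keeps staying on any anticoagulant apart from staying on the assigned one, but does not say which of the two defines the subgroup.

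Protocol 12.6 covers what happens after a new VTE. For a patient taking a DOAC without interruption, "it is recommended that they switch to a parenteral agent/standard of care". For warfarin it suggests a parenteral agent. For a patient on a full-dose parenteral agent, "then we suggest escalating the dose to 125" per cent. The first takes the patient out of Arm 1; the other two keep the patient on Arm 2 drugs. Sites may also switch or discontinue in either arm.

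**The concern.** A subgroup effect is a randomized comparison only if the subgroup could have been fixed before assignment. Here the endpoint can decide the stratum: a patient who recurs in month 2 and then changes or stops treatment is classed as a poor persister because of the recurrence. Bleeding and death can do the same, and SAP 3.9 extends the subgroup analyses to those endpoints. If the days are counted over a fixed 180, every death before day 144 falls outside the >80% stratum.

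The sorting can also differ by arm, because the advice in protocol 12.6 moves only DOAC patients out of their assigned class.

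What is at stake is interpretation. SAP 3.5.2.1 gives better adherence as the reason to expect fewer recurrences on DOAC. Readers will naturally take a favorable result among good persisters as confirmation of that rationale.

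**Working it through.** **The plan's own figures.** None is given for these strata. The nearest is the expected interval length of 6.1 points at 668 randomized (SAP 2.5). Scaling gives 6.1 x sqrt(668/750) = 5.76, which matches the 5.8 in the 750-patient row. The event rates behind the table are not stated. With equal rates and 334 per arm, the length is 2z x sqrt(2p(1-p)/334). Setting this to 0.061 gives p = 6.1% for z = 1.645 and 5.6% for z = 1.710. A 6% risk is therefore consistent with the documents.

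**Assumptions not in the documents.** No true effect; recurrence risk p in both arms; recurrence times uniform over 180 days; a 180-day denominator; underlying persistence unrelated to risk; deaths ignored; a share s of recurrences ends the therapy being counted. Since 0.8 x 180 = 144, ending therapy before day 144 leaves at most 80% of days, and 80% of recurrences fall before that day.

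**Reading 1: days on assigned therapy.** Observed risk in the >80% stratum:

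R = p(1 - 0.8s) / [(1 - p) + p(1 - 0.8s)]

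At p = 6%:
- s = 0.8: 0.0216 / 0.9616 = 2.25%
- s = 0.5: 0.0360 / 0.9760 = 3.69%
- s = 0.2: 0.0504 / 0.9904 = 5.09%

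At p = 8%:
- s = 0.8: 0.0288 / 0.9488 = 3.04%
- s = 0.2: 0.0672 / 0.9872 = 6.81%

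| Risk | s, DOAC vs Arm 2 | False difference, >80% stratum |
|---|---|---|
| 6% | 0.5 vs 0.2 | 3.69 - 5.09 = -1.4 points |
| 6% | 0.8 vs 0.2 | 2.25 - 5.09 = -2.8 points |
| 8% | 0.8 vs 0.2 | 3.04 - 6.81 = -3.8 points |

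In the limiting case where no Arm 2 recurrence leaves Arm 2 drugs, 50% switching on DOAC at 6% gives 3.69 - 6.00 = -2.3 points. A simulation of that case (335 per arm, 65% underlying >80% persistence, 4000 replicates) gave -2.45 points, with the upper 90% limit below zero in 33% of null trials against a nominal 5%. The strata at or below 80% showed the mirror image, +4.3 points.

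**Reading 2: days on any anticoagulant.** A switch to a parenteral agent still counts as persistent, so the arm-specific advice moves nobody. Let a share s of recurrences stop all treatment in both arms, and let q be the proportion who would exceed 80% without an event. In the >80% stratum q cancels, so the difference is 0. In the simulation the upper limit then fell below zero in about 5% of null trials. In the combined lower strata:

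R = [(1 - q)p + 0.8s x qp] / [(1 - q) + 0.8s x qp]

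With p = 6%, and q = 0.7 on DOAC against 0.5 in Arm 2:
- s = 0.25: 0.0264 / 0.3084 = 8.56% vs 0.0360 / 0.5060 = 7.11%, or +1.4 points
- s = 0.50: 0.0348 / 0.3168 = 10.98% vs 0.0420 / 0.5120 = 8.20%, or +2.8 points

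The direction of the gap in q follows the SAP's expectation of better DOAC adherence; its size is assumed.

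**The case against.** The strongest reply is that the literal wording favors reading 2. The subgroup omits the word assigned, SAP 3.7 uses it when it is meant, and protocol 11.5 collects days off all anticoagulants. On that reading the >80% row carries essentially no false difference from the advice in protocol 12.6. This stands, and it rules out any unconditional claim about that row. It does not clear the lower rows, which the plan also displays.

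The advice in 12.6 is not binding, and the switching and stopping shares are assumed. This stands too: the sizes above are illustrations, not predictions.

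The analyses are labelled exploratory, no confirmatory claim rests on them, and under reading 1 a false benefit in the top row would sit beside a false harm below it. This limits the consequence. But the label deals with multiplicity, whereas the problem here is bias, which no caution about chance findings addresses.

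It may be said that defining the variable, counting days only to the first event and adding a caveat would suffice. That removes the direct path from outcome to stratum, but patients are still selected on behavior after randomization, so a treatment-effect label remains unsupported.

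A reader might extend the criticism to the row "Participants treated with bevacizumab". The documents do not support that. They leave the timing of that treatment unspecified, but they show no route by which a recurrence or the assigned arm would determine it.

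**Conclusion.** The point holds as a defect of design. The plan estimates treatment effects within strata that the outcome can alter, and does not fix which persistence is meant. With no true effect and 6% risk, the false difference is about -1.4 to -2.8 points in the >80% stratum under the assigned-therapy reading with 50 to 80% against 20% switching. It reaches -3.8 at 8% risk with 80% against 20%. Under the any-anticoagulant reading it is about 0 there, and about +1.4 to +2.8 in the lower strata if 25 to 50% of recurrences in both arms stop treatment and underlying persistence is 70% against 50%. All of this rests on uniform event times, a 180-day denominator and assumed shares. For bleeding and death the mechanism is reasoned, not quantified.

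A reader might infer that the plan will produce a false DOAC benefit of 3 points. The documents do not support that: it needs the less literal reading together with switching shares that appear nowhere in them. Nor do these rows touch the primary noninferiority or superiority test. The change is worth making, but it is not critical to the trial's main conclusion.

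**What to change.** Remove both persistence rows from the treatment-effect subgroups in SAP 3.9.4 and protocol 13.5.1.4, and from the forest plots. Report persistence by arm descriptively, as SAP 3.7 already plans.

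If a link between persistence and outcome is wanted, specify four things:
- whether persistence means any anticoagulant or the assigned therapy;
- a landmark, for example day 90, with patients classified by persistence up to that day among those alive and event-free;
- that only later events count;
- that the result is labelled an association, not a treatment effect.

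The cost is SAP and protocol wording and two exploratory forest-plot rows. The landmark version also gives up events before day 90 and still conditions on behavior after randomization, hence the label. No new data are needed, and the management advice in protocol 12.6 is not affected.
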